## 2 PROTOCOL SYNOPSIS

Title	Phase I/II clinical trial of Daratumumab in patients with relapsed acute myeloid leukemia post-allogeneic hematopoietic stem cell transplant.
Protocol Short Title	Daratumumab in post-transplant relapse
Name of Drug	Daratumumab
Study Rationale	

1. IFN-<math>\gamma</math> promotes graft-versus-leukemia effects without directly interacting with leukemia cells in mice after allogeneic hematopoietic cell transplantation.

2. Endogenous IFN-gamma levels are elevated in post-transplant patients post-conditioning, infections, GVHD, and during hematopoietic regeneration.

3. We hypothesize that (i) IFN-gamma levels will be higher in post-transplant patients than healthy donors (ii) combination of Daratumumab and endogenous IFN-gamma will mediate antileukemic efficacy post-transplant (iii) the combination of Dara and donor lymphocytes will provide potent effectors, recruit effectors to marrow and mediate GVL.

Treatment Duration	8 weeks; Daratumumab may be continued beyond 8 weeks if clinical benefit is observed up to 12 months.
Dosing Schedule	Weekly Dara for 8 doses
Route	Intravenous
Age range	$\geq 18$ years
Study Duration	10 months to 3.5 years for phase I; 24 months for phase II.
Sample size	8-40 patients for Phase I; 25 patients for phase II
Inclusion Criteria	

1. Patients <math>\geq 18</math> years

2. AML relapse following Allo-HSCT (Morphological relapse, or MRD positive verified by flow cytometry, cytogenetics, and molecular mutations)

Date of protocol: 10/14/2020

IRB Approval Date: 11/24/2020

Version of protocol: 7

IND number: 139015

Institutional protocol number: OSU 17102

	

3. For patients in Dose level 1 (Daratumumab only), relapsed refractory AML patients who have previously not received an allogeneic HCT are eligible.

4. Patients with R/R AML must not be candidates for available therapies known to be effective for treatment of their AML.

5. MDS transformed to AML following Allo-HCT

6. Patients who received a 10/10 HLA-matched allogeneic HCT either from sibling donors or unrelated donors or atleast a 5/10 haploidentical transplant for dose levels needing DLI

7. Engraftment must have occurred as defined by platelet (PLT) count <math>> 20,000/\mu\text{L}</math> and ANC <math>\geq 0.5</math>

8. ECOG performance status <math>< 3</math>

9. Creatinine clearance <math>> 40 \text{ ml/min}</math> (Calculated or measured)

10. Aspartate aminotransferase (AST) <math>< 3 \times</math> upper limit of normal (ULN), alanine aminotransferase (ALT) <math>< 3 \times</math> ULN, and total bilirubin <math>< 1.5 \times</math> ULN

11. Off calcineurin inhibitors for at least 2 weeks

12. Prednisone dose <math>\leq 20 \text{ mg/day}</math>

13. Patients with proliferative disease can be cytoreduced with cytotoxic chemotherapy at investigator's discretion, but there should be at least a 14 day window between start of cytoreductive therapy and start of Daratumumab

14. Blast count <math>< 20\text{K}/\text{day}</math> (hydrea use is allowed)

15. Female patients of childbearing potential who are sexually active must be willing to use an effective barrier method of birth control to avoid pregnancy during the study and for a minimum of 3 months after stopping study treatment

16. Male patients must agree to not donate sperm and if sexually active with partners of childbearing potential must be willing to use an effective barrier

--	---

Date of protocol: 10/14/2020

IRB Approval Date: 11/24/2020

Version of protocol: 7

IND number: 139015

Institutional protocol number: OSU 17102

	
method of birth control to avoid pregnancy during the study and for a minimum of 3 months after stopping study treatment

Exclusion Criteria	

1. No demonstrable evidence of donor chimerism (< 55% donor CD3 or CD33 chimerism)

2. Patients with a molecular mutation without chromosomal abnormalities or declining chimerisms (MRD status must be verified by surface marker and mutational analyses)

3. Active graft-versus-host disease (GVHD) grades I-IV; prior acute GVHD could have occurred but resolved at time of initiation of Daratumumab

4. Extensive chronic GVHD requiring ongoing immunosuppression with calcineurin inhibitors or more than 20 mg of prednisone

5. Patients with FLT3+ AML or blast crisis CML who have not yet received post-transplant TKI therapy

6. Active CNS or testicular disease

7. Subject is: seropositive for human immunodeficiency virus (HIV); seropositive for hepatitis B (defined by a positive test for hepatitis B surface antigen [HBsAg]). Subjects with resolved infection (ie, subjects who are HBsAg negative but positive for antibodies to hepatitis B core antigen [anti-HBc] and/or antibodies to hepatitis B surface antigen [anti-HBs]) must be screened using real-time polymerase chain reaction (PCR) measurement of hepatitis B virus (HBV) DNA levels. Those who are PCR positive will be excluded. EXCEPTION: Subjects with serologic findings suggestive of HBV vaccination (anti-HBs positivity as the only serologic marker) AND a known history of prior HBV vaccination, do not need to be tested for HBV DNA by PCR.; seropositive for hepatitis C (except in the setting of a sustained virologic response [SVR], defined as aviremia at least 12 weeks after completion of antiviral therapy).

Date of protocol: 10/14/2020

IRB Approval Date: 11/24/2020

Version of protocol: 7

IND number: 139015

Institutional protocol number: OSU 17102

	

8. Patients must not have chronic obstructive pulmonary disease with a forced expiratory volume in 1 second (FEV1) < 50% of predicted normal. FEV1 is required for patients suspected of having chronic obstructive pulmonary disease and are not eligible if FEV1 is < 50% of predicted normal.

9. Patients must not have moderate or severe persistent asthma within the past 2 years and must not have currently uncontrolled asthma of any classification.

10. History of grade IV anaphylactic reaction to monoclonal antibody therapy

11. Active autoimmune disease prior to transplant

12. Pregnancy

13. Female patients of childbearing potential who are sexually active and unwilling to use an effective barrier method of birth control to avoid pregnancy during the study and for a minimum of 3 months after study treatment

14. Male patients who wish to donate sperm or with partners of childbearing potential who are sexually active and unwilling to use an effective barrier method of birth control to avoid pregnancy during the study and for a minimum of 3 months after study treatment

15. Concurrent use of any other investigational drugs

Study Design	

1. Phase I study (3+3 study design) with the following dose levels: For related sibling donors:

a. Dose level 1: Dara 16mg/kg

b. Dose level 2: Dara 16mg/kg + DLI at weeks 3-5: 1x10e6 CD3/kg

c. Dose level 3: Dara 16mg/kg + DLI at weeks 3-5: 1x10e7 CD3/kg

 For unrelated donors:

Date of protocol: 10/14/2020

IRB Approval Date: 11/24/2020

Version of protocol: 7

IND number: 139015

Institutional protocol number: OSU 17102

	

d. Dose level 1: Dara 16mg/kg

e. Dose level 2: Dara 16mg/kg + DLI at weeks 3-5: 1x10e5 CD3/kg

f. Dose level 3: Dara 16mg/kg + DLI at weeks 3-5: 1x10e6 CD3/kg

 
For haploidentical donors:
 

g. Dose level 1: Dara 16mg/kg

h. Dose level 2: Dara 16mg/kg + DLI at weeks 3-5: 1x10e4 CD3/kg

i. Dose level 3: Dara 16mg/kg + DLI at weeks 3-5: 1x10e5 CD3/kg

 
2. Phase II study with maximal tolerated dose as established for both related and unrelated donors. The MTD for the DLI may be different for related and unrelated donors.

Study logistics	

1. Identify patient with suspected relapse

2. Trial discussed, consent obtained and bone marrow performed

3. If MRD positive or morphologic relapse, stop immunosuppression within a week of biopsy results

4. If no evidence of GVHD in 2 weeks after stopping immunosuppression, start Daratumumab.

5. Daratumumab may be given as outpatient or inpatient depending on treating physician discretion.

6. Patient will be seen prior to every Daratumumab dose and assessment for GVHD will be done

7. Plan bone marrow biopsy after doses 3 and before dose 4.

8. Administer DLI between weeks 3-5.

9. Resume weekly Dara weeks 6-8

Date of protocol: 10/14/2020

IRB Approval Date: 11/24/2020

Version of protocol: 7

IND number: 139015

Institutional protocol number: OSU 17102

	10. Bone marrow biopsy after week 8
Study Objectives – Phase I	
Primary Objectives:
 
1. Phase I: To determine the maximum tolerated dose (MTD) of Daratumumab and escalating doses of donor lymphocyte infusions (DLI) in post-HCT patients with relapsed AML and MDS transformed to AML.
 
2. Phase II: To evaluate overall response rate to Daratumumab and DLI by week 8 in patients with post-HCT relapsed AML and MDS
 
Secondary Objectives:
 

1. To assess overall response rates in MRD positive patients and in patients with overt morphological relapse

2. To assess MRD conversion rates from MRD positive to MRD negative.

3. To determine the post-relapse 6-month OS rates of patients with relapsed AML and MDS following allo-HSCT who are treated with Daratumumab

4. To determine the rates of GVHD (both grades II-IV and III-IV) and autoimmune side effects of Daratumumab by 3 months.

5. To determine the post-relapse 6-month PFS rates of patients with relapsed AML and MDS following allo-HSCT who are treated with Daratumumab

Safety Assessment	Physical examination, electrocardiogram (ECG), clinical laboratory tests (hematology, blood chemistries, urinalysis, prothrombin time [PT], activated partial thromboplastin time [APTT]), anti-drug antibody (ADA), cytokine/inflammatory factor levels, vital signs, and adverse event/toxicity assessment.
Efficacy Assessment	Standard response assessment as defined for AML, duration of response, and overall survival/PFS.

Date of protocol: 10/14/2020

IRB Approval Date: 11/24/2020

Version of protocol: 7

IND number: 139015

Institutional protocol number: OSU 17102

DLT definition	

• Acute GVHD <math>\geq</math> Grade 3

• Any non-hematologic toxicity <math>\geq</math> Grade 3 related to Daratumumab

• Hematologic toxicity: grade 4 toxicity not related to the underlying disease and not responding to growth factor or transfusion within 7 days

• Grade 3 or higher non-neurologic immune-related adverse events (e.g. diarrhea, pruritus, rash) that responds to corticosteroids and improve to grade 1 or less within 4 weeks will NOT count as DLTs. Optional biopsy of affected organs will be encouraged to help determine whether the immune-related condition is due to GVHD

Enrollment schedule	
Dose level 1: Weekly Dara for eight doses; if no infusional toxicity observed or GVHD observed, proceed to next dose level. 3 patients at a time can be enrolled in one dose level.
 
If no GVHD is observed after at least 2 weeks after DLI, enrollment will proceed to next dose level.

Definitions for safety-evaluability	Received at least one dose of Daratumumab
Definition for DLT evaluability	
All patients are evaluable for DLT except patients who are unable to receive 3 doses of daratumumab in dose level 1, or 3 doses of daratumumab and DLT for dose levels 2 and 3 due to progression of AML.
 
DLT observation period will be from the first dose of daratumumab till 7 days post 3rd dose of daratumumab (for dose level 1) and from the first dose of daratumumab till at least 4 weeks post DLI (for dose level 2 and 3)

Definitions for efficacy evaluability:	All eligible patients who receive at least one dose of Daratumumab, do not withdraw consent, and are evaluated for response at week 8.
Dose-limiting toxicity:	Grade 3 or 4 GVHD
Special situations	

1. If patients attain response before DLI, there will be three options at the discretion of treating physician :

a. Proceed with DLI

Date of protocol: 10/14/2020

IRB Approval Date: 11/24/2020

Version of protocol: 7

IND number: 139015

Institutional protocol number: OSU 17102

	

b. Continue Daratumumab maintenance( If Daratumumab is given as maintenance, a schedule of 16mg/kg every 2 weeks for 16 (8 doses) weeks and then monthly for 6 months will be administered)

c. Proceed with second transplant.

 
2. If patients develop steroid-responsive GVHD and remission before DLI, there will be two options at the discretion of treating physician :
 

a. Continue Daratumumab maintenance (If Daratumumab is given as maintenance, a schedule of 16mg/kg every 2 weeks for 16 weeks (8 doses) and then monthly for 6 months will be administered)

b. Proceed with second transplant.

--	---

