## 7 STUDY DESIGN

### 7.1 OVERVIEW OF STUDY DESIGN

This is a phase I/II study that evaluates combination of Daratumumab and escalating doses of donor lymphocyte infusions. Donor lymphocyte infusions will be given within 72 hrs. of daratumumab dose. The following dose levels are used.

1. Phase I study with the following dose levels for related sibling donors:
  - a. Dose level 1: Dara 16mg/kg
  - b. Dose level 2: Dara 16mg/kg + DLI (1 infusion at any time between weeks 3-5) : 1x10e6 CD3/kg
  - c. Dose level 3: Dara 16mg/kg + DLI (1 infusion at any time between weeks 3-5): 1x10e7 CD3/kg
2. Phase I study with the following dose levels for unrelated donors:
  - c. Dose level 1: Dara 16mg/kg
  - d. Dose level 2: Dara 16mg/kg + DLI (1 infusion at any time between weeks 3-5): 1x10e5 CD3/kg
  - e. Dose level 3: Dara 16mg/kg + DLI (1 infusion at any time between weeks 3-5): 1x10e6 CD3/kg
3. Phase I study with the following dose levels for haploidentical donors:
  - f. Dose level 1: Dara 16mg/kg
  - g. Dose level 2: Dara 16mg/kg + DLI (1 infusion at any time between weeks 3-5): 1x10e4 CD3/kg
  - h. Dose level 3: Dara 16mg/kg + DLI (1 infusion at any time between weeks 3-5): 1x10e5 CD3/kg

Patients with MRD will not be enrolled until the DLT period for dose level 1 has been completed and it has been determined that the treatment schedule is safe. Patients must be positive for MRD disease as

Date of protocol: 10/14/2020

IRB Approval Date: 11/24/2020

Version of protocol: 7

IND number: 139015

Institutional protocol number: OSU 17102

[figure not shown]
determined by the combined analyses of flow cytometry, genomic sequencing and cytogenetics. Patients who do not demonstrate evidence of MRD in all three methods will not be eligible for the trial.

Bone marrow biopsies are done at the completion of 8 weeks. The maximal tolerated dose of DLI is chosen for expansion to the phase II portion of the study.

If patients are found to be in CR at the end of 8 weeks and treating physician concludes that patient continues to benefit from treatment, patients may proceed to Daratumumab maintenance with a schedule of 16mg/kg every 2 weeks for 16 weeks (8 doses) and then monthly for 6 months .

For patients with rapidly progressive disease despite 4 doses of Daratumumab, they will come off trial.

The dose level that is deemed safe will be chosen for the phase II portion of the study.

Dose level	Sibling donor	Unrelated donor	Haploidentical donor

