## 9.3 DONOR LYMPHOCYTE INFUSION

Donor lymphocytes are typically infused as outpatient according to institutional guidelines. To allow for scheduling ease, DLI will be infused within 72 hrs. after the daratumumab dose, anytime between week 3-4. .

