## 16 STATISTICAL CONSIDERATIONS

Study design/Sample size

This is a phase I/II study evaluating the combination of Daratumumab and escalating doses of DLI in patients with relapsed AML or transformed from MDS to AML post allo-HCT. Three dose levels will be used for related sibling donors and unrelated donors respectively.

Study Design: The standard 3+3 design will be applied to determine MTD of donor lymphocyte infusion when given with a fixed dose of Daratumumab. The dose escalation process for related sibling donor and unrelated donor will be conducted concurrently, but separately.

Dose escalation will proceed within each cohort according to the following scheme.

Number of Subjects with DLT at a Given Dose Level	Escalation Decision Rule
0 out of 3	Enter 3 subjects at the next dose level.
1 out of 3	
Enter 3 more subjects at this dose level.
 

• If 0 of these 3 subjects experience DLT, proceed to the next dose level.

• If 1 or more of this group suffer DLT, then dose escalation is stopped, and this dose is declared the maximally administered dose. Three (3)

Date of protocol: 10/14/2020

IRB Approval Date: 11/24/2020

Version of protocol: 7

IND number: 139015

Institutional protocol number: OSU 17102

	additional subjects will be entered at the next lowest dose level if only 3 subjects were treated previously at that dose.
>2	Dose escalation will be stopped. This dose level will be declared the maximally administered dose (highest dose administered). Three (3) additional subjects will be entered at the next lowest dose level if only 3 subjects were treated previously at that dose.
<1 out of 6 at highest dose level below the maximally administered dose	This is generally the recommended maximally tolerated dose.

The MTD will be defined as the highest safely tolerated dose where at most one patient in six experiences DLT during DLT observation period. The DLT observation period is defined as below.

Dose Level	DLT observation period
1	From the first dose of Daratumumab till 7 days post 3 rd dose
2/3	From the first dose of Daratumumab till at least 4 weeks post DLI

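### The daratumumab schedule around DLI contradicts itself (eight weekly doses, or a resumption in weeks 6-8), and the sections disagree on whether DLI may be given in week 5

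*Combined protocol and SAP*

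**What the plan says.** **Daratumumab.** The Dosing Schedule row of the synopsis (section 2) reads "Weekly Dara for 8 doses" and is not limited to any dose level. The Enrollment schedule row repeats the count for the first level only: "Dose level 1: Weekly Dara for eight doses". The Study logistics row sets a sequence: "Plan bone marrow biopsy after doses 3 and before dose 4", then DLI in weeks 3-5, then "Resume weekly Dara weeks 6-8". No section says that doses are held around DLI, or which ones. The study calendar (section 12.1.3) has weekly visits through week 8 but no row for daratumumab administration in those weeks.

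**DLI window.** The synopsis and the dose-level table in section 7.1 give weeks 3-5, and the list in section 7.1 allows "1 infusion at any time between weeks 3-5". Section 9.3 says "DLI will be infused within 72 hrs. after the daratumumab dose, anytime between week 3-4". The calendar carries one DLI mark, in the week 4 column, and its note treats week 4 as one possibility.

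**72-hour link.** Section 7.1 says "Donor lymphocyte infusions will be given within 72 hrs. of daratumumab dose", with no direction. Section 9.3 requires DLI to come after the dose.

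**What rests on this.** Section 16 describes the phase I aim as to "determine MTD of donor lymphocyte infusion when given with a fixed dose of Daratumumab". The phase II primary objective is response by week 8 to daratumumab and DLI.

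**The concern.** Two physicians who each follow the protocol could treat patients at the same dose level differently: one gives daratumumab through weeks 4 and 5, the other stops after dose 3 and restarts in week 6. One could give DLI in week 5 under section 7.1, and section 9.3 would count that as a deviation.

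Escalation decisions rest on three to six patients per level, so a few patients treated under different readings would blur which schedule an MTD was established for. The ambiguity carries into phase II, because section 16 adds the three to six phase I patients treated at the MTD to the response analysis.

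**Working it through.** **Inputs.** From the calendar: weeks 1 to 8 start on days 1, 8, 15, 22, 29, 36, 43 and 50, and the final marrow is in the day 57-71 column. From sections 2 and 7.1: 16 mg/kg per dose. From section 16: at levels 2 and 3 the DLT period ends no earlier than 28 days after DLI.

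**Step 1. Dose count.**
- Uninterrupted weekly dosing, days 1 to 50: (50 − 1)/7 + 1 = 8 doses, which reproduces the plan's figure. Total 8 × 16 = 128 mg/kg.
- Pause reading, weeks 1-3 and 6-8: 3 + 3 = 6 doses. Total 6 × 16 = 96 mg/kg. Shortfall (8 − 6)/8 = 25%.
- Holding week 3 as well would leave 5 doses, but the logistics place a marrow after dose 3 and the calendar note requires that marrow before DLI. I set this reading aside.

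**Step 2. The 72-hour link.** Lag = (DLI day − day of last dose) × 24 h.

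| DLI day | Uninterrupted: h since last dose | Pause: h since last dose | Pause: h to day-36 dose |
|---|---|---|---|
| 15 (week 3) | 0 | 0 | 504 |
| 22 (week 4) | 0 | 168 | 336 |
| 29 (week 5) | 0 | 336 | 168 |
| 33 (week 5) | 96 | 432 | 72 |
| 35 (week 5) | 144 | 480 | 24 |

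- Pause reading: the shortest lag in weeks 4-5 is 168 h, so section 9.3's *after* fails on every day of those weeks. Section 7.1's *of* is met only when 36 − day ≤ 3, that is on days 33-35. A week-3 DLI on days 15-18 meets both wordings.
- Uninterrupted reading: *after* is met on days 15-18, 22-25 and 29-32. *Of* is met on every day of weeks 3-5, because with doses seven days apart no day is more than three days from one. The link works in each week, but there is then nothing to resume in week 6.

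Neither reading agrees with all the text.

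**Step 3. The DLI window.** Weeks 3-5 (synopsis, section 7.1) against weeks 3-4 (section 9.3). The calendar's week-4 mark lies inside both, so the conflict is week 5 alone.

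**Step 4. What shifts between patients.**

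| DLI day | Earliest end of DLT period (DLI + 28) | Doses inside it, uninterrupted | Doses inside it, pause |
|---|---|---|---|
| 15 | day 43 | 7 | 5 |
| 22 | day 50 | 8 | 6 |
| 29 | day 57 | 8 | 6 |

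Time from DLI to the final marrow:
- DLI on days 15-18: 57 − 18 = 39 to 71 − 15 = 56 days.
- DLI on days 29-32: 57 − 32 = 25 to 71 − 29 = 42 days.

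The two ranges overlap.

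**Step 5. The phase II design.** With n = 25 and rejection at 6 or more responses, P(X ≥ 6) is 0.033 at a 10% response rate and 0.807 at 30%. Neither depends on the schedule.

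**The case against.** The best defence is that the pause hangs on one word. No section states a hold, and much of the text fits uninterrupted dosing: the eight-dose row, weekly visits through day 50, and a 72-hour rule that presupposes a dose near DLI. *Resume* may be loose drafting for *continue*. This stands to the extent that the six-dose count and the 72-hour failure are conditional. It does not remove the contradiction, because the instruction is in the current text and nothing else in the document overrides it.

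It is also fair to say that variable DLI timing is declared flexibility. Section 9.3 gives scheduling as the reason, and the DLT period is anchored to DLI, so every DLI recipient has the same minimum follow-up afterwards. A moving end date is by design. Section 16.2 also plans a response rate among patients with at least three doses plus DLI, and a summary of dose modifications and delays. None of this says whether doses are due in weeks 4 and 5.

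Some stronger readings are tempting but unsupported:
- That there are three conflicting DLI windows. There are two; the calendar mark fits both.
- That the 72-hour link cannot be met at all in weeks 4-5. It can under uninterrupted dosing, and on days 33-35 under section 7.1 even with a pause.
- That different sites would diverge. Accrual, infusion medication and GVHD management all point to one institution, so the risk lies between treating physicians.
- That section 16's fixed daratumumab dose is a statement about the number of doses. It most naturally means 16 mg/kg at every level.

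**Conclusion.** The concern holds as a contradiction in the dosing instructions, with two firm parts. First, eight weekly doses and a resumption in weeks 6-8 do not fit together, and the calendar does not decide between them. Second, week-5 DLI is permitted by sections 2 and 7.1 and excluded by section 9.3.

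The size is conditional. If *resume* means that weeks 4-5 are held, levels 2 and 3 receive 25% fewer planned doses and section 9.3's link fails throughout weeks 4-5. If dosing is uninterrupted, neither consequence follows. This assumes dosing on the calendar's nominal days.

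The effect is on what the MTD and the week-8 response refer to. A reader might infer that the phase II sample size or decision rule is undermined; neither is. Nor does the document show that patients have in fact been treated differently. It shows only that the text allows it.

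**What to change.** Reconcile the synopsis (Dosing Schedule, Study Design and Study logistics rows), section 7.1 with its dose-level table, section 9.3 and the calendar in section 12.1.3, so that they give:

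1. one daratumumab schedule through the DLI weeks, stating whether any doses are held and which, and the planned number of doses at levels 2 and 3;
2. one DLI window;
3. one wording of the 72-hour link, *of* or *after*, checked against every permitted DLI day;
4. a daratumumab administration row in the calendar.

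Which schedule and which window apply is for the sponsor to decide; this review takes no position. The cost is an amendment to wording and one calendar row, with a small loss of scheduling flexibility.

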If a patient in dose level 1 receives less than 3 doses of Daratumumab due to reasons other than toxicity, then this patient will not be evaluable for DLT and will be replaced. An additional patient will be added to the dose cohort. For dose level 2 or 3, if a patient does not receive 3 doses of Daratumumab and DLI due to reasons other than toxicity, then this patient will not be evaluable and will be replaced. There will be no intrapatient dose escalation. Phase I may involve as few as 3 patients (three at the starting dose level if  $\geq 2$  DLTs are experienced) and a maximum of 18 patients will be treated, six at each of the 3 dose levels. We assume that 10% of the patients in this group will not be evaluable due to not finishing the DLT observation period. So we expect to accrue a minimum of 4 patients and a maximum of 20 patients.

At OSU, 125 patients with AML/MDS underwent allo-HSCT in 2012 and 2013. Among these, 32 patients relapsed. About 40% were from related donor and 60% from unrelated donor. So we expect to accrue approximately 6 patients for the related sibling donor cohort and 10 patients for the unrelated donor cohort per year. Hence, the minimum study duration for phase I would be about 8-10 months and the maximum study duration would be around 2.5-3.5 years (accounting for the DLT observation period) for related sibling donors and unrelated donors respectively.

After the MTD has been established, we will expand to Phase II trial. For phase II part, considering that patients receiving transplant from related sibling donor or unrelated donor with each treated at the corresponding MTD of Daratumumab plus DLI are expected to have similar profiles for response and toxicities, we will combine these 2 cohorts together in phase II stage. The null hypothesis is that combination of Daratumumab and DLI has a response rate of < 10% in patients with relapsed AML following allo-HSCT. The alternative hypothesis is that Daratumumab has a response rate of at least 30% in patients with relapsed AML following allo-HSCT. With a type 1 error (alpha): 0.05, and a type 2 error (beta = 1 – power): 0.20, the sample size would be 25 patients for Phase II. If the number of patients achieving ORR is 6 or more, then we reject the null hypothesis. We would include 3-6 patients from

Date of protocol: 10/14/2020

IRB Approval Date: 11/24/2020

Version of protocol: 7

IND number: 139015

Institutional protocol number: OSU 17102

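### The synopsis enrollment row gives its own go-ahead for the next dose level, which conflicts in both directions with the DLT-count 3+3 rule in section 16

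*Combined protocol and SAP*

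**What the plan says.** Two places state when the next dose level opens.

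The synopsis (section 2), row Enrollment schedule, has one sentence per stage. For level 1, daratumumab alone: "if no infusional toxicity observed or GVHD observed, proceed to next dose level". For the levels with DLI: "If no GVHD is observed after at least 2 weeks after DLI, enrollment will proceed to next dose level". The row gives no GVHD grade, no count of patients with DLT, no expansion step and no reference to section 16.

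Section 16 states: "Dose escalation will proceed within each cohort according to the following scheme". The scheme is a table keyed to the number of subjects with DLT. None of three opens the next level. One of three leads to "Enter 3 more subjects at this dose level", and the next level opens only if none of those three has a DLT. The stop at two or more is confirmed by the sample-size text after the table: the sentence beginning "Phase I may involve as few as 3 patients (three at the starting dose level if" goes on to name two or more DLTs. The synopsis Study Design row carries the matching label: "Phase I study (3+3 study design) with the following dose levels".

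DLT is itself defined in two ways. The synopsis row DLT definition and the bullets in section 9.6 list severe acute GVHD, daratumumab-related non-hematologic toxicity of grade 3 or higher, and grade 4 hematologic toxicity that is not disease-related and does not respond within 7 days. A later synopsis row, headed Dose-limiting toxicity, says only "Grade 3 or 4 GVHD", and the opening sentence of section 9.6 also names GVHD alone.

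**The concern.** Both texts govern the same decision and use different criteria. The synopsis sentences are worded as an operative go-ahead, not as a summary of a rule found elsewhere. A study team working from the synopsis could open level 3 after a level 2 cohort that section 16 would expand or close, so that patients enter the higher DLI dose before the DLT count is resolved. Or it could hold at a level that section 16 would clear. The phase I primary endpoint in section 16.1 is the maximum tolerated dose (MTD), and either departure changes which doses are studied and on how many patients.

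**Working it through.** **1. The plan's own phase I figure.** Section 16 has 3 levels with up to 6 patients each, so 3 × 6 = 18 evaluable patients at most and 3 at least, per donor cohort. With 10% not evaluable for DLT: 3 / 0.9 = 3.33, rounded up to 4, and 18 / 0.9 = 20. This reproduces the stated 4 to 20. The maximum relies on the expand-to-six step, which exists only in section 16.

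**2. Where each synopsis sentence applies.** The level 1 sentence governs the step from level 1 to level 2. Level 3 is the highest level, so the post-DLI sentence governs only the step from level 2 to level 3.

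**3. The two rules side by side, under the full DLT list.** Each row describes the first three evaluable patients, with no other events.

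| Cohort | Synopsis row | Section 16 |
|---|---|---|
| Level 2, no GVHD, no DLT | proceed | proceed |
| Level 2, no GVHD, 1 non-GVHD DLT | proceed | add 3 patients |
| Level 2, no GVHD, 2 or 3 with non-GVHD DLT | proceed | stop |
| Level 2, grade 1-2 GVHD, no DLT | go-ahead withheld | proceed |
| Level 1, grade 1-2 infusion reaction, no DLT | go-ahead withheld | proceed |
| Level 1, 1 grade 3 infusion reaction counted as DLT | go-ahead withheld | add 3 patients |

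Rows 2 and 3 are the permissive conflict. Rows 4 and 5 are the restrictive one: the synopsis blocks on GVHD of any grade, and at level 1 on infusional toxicity of any grade, whereas only grade 3-4 GVHD and daratumumab-related non-hematologic toxicity of grade 3 or higher are DLTs. In row 6 neither text escalates.

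**4. Is a non-GVHD DLT foreseeable at level 2?** Section 9.2 provides for grade 3 infusion reactions. Daratumumab is given at every level, and the observation period at levels 2 and 3 starts with its first dose. Such a reaction is a DLT under the full list unless it is excused as an immune-related event that responds to corticosteroids and improves to grade 1 or less within 4 weeks. The hematologic route is narrow, because sections 10.1 and 11.2 attribute cytopenias largely to the leukemia.

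**5. Does the GVHD-only definition remove the conflict?** It would remove rows 2 and 3, because no non-GVHD event would then be a DLT. It fits the rest of the plan poorly. Inclusion criterion 5 in section 8.1 admits patients at level 1 who have never had an allogeneic transplant. With no donor graft they cannot develop GVHD, so a GVHD-only definition would leave them with no possible DLT. The adverse event form in the appendix also records DLT alongside attribution to disease, daratumumab, transplant or DLI. The full list is the better reading. The restrictive conflict in rows 4 and 5 exists under either definition.

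**6. Timing.** The synopsis row waits at least 2 weeks after DLI; the section 16 DLT observation period runs to at least 4 weeks after DLI. The same correction settles this difference.

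**The case against.** The best defence is that the row is only an enrollment summary and section 16 plainly governs. The synopsis labels the design 3+3 and gives the full DLT list in the row directly above. It also defines DLT evaluability and an observation period, which would serve little purpose if absence of GVHD alone cleared a level. Only section 16 has expand and stop steps. Section 14.1 requires weekly safety calls, and section 16.3 expects a review right after the DLT window of the third patient in each cohort. This stands as far as likely practice goes: a careful team would probably follow section 16. It does not remove the conflict. No text gives section 16 precedence, the section 16.3 review has no decision rule of its own, and the enrollment holds in sections 9.6 and 14.1 are triggered by GVHD.

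A second objection concerns the consequence. Daratumumab is 16 mg/kg at every level and only DLI rises. The omitted non-hematologic events are by definition related to daratumumab, so moving up leaves that exposure unchanged. The synopsis does gate on GVHD, the hazard most plausibly linked to the DLI dose, and more strictly than the DLT definition. This also stands, and it limits what can be claimed.

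A reader might infer three stronger things that the documents do not support:

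- That the synopsis rule is simply the laxer one. The table above shows that it is stricter for mild GVHD and for mild level 1 infusion reactions.
- That a probability of wrong escalation can be given. The documents state neither a GVHD rate nor a non-GVHD DLT rate for this regimen, so any percentage would only reflect assumed inputs.
- That the stop row, as printed, leaves exactly two DLTs without a rule. The sample-size text states two or more, so the printed sign is most likely a lost greater-than-or-equal sign.

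**Conclusion.** The inconsistency is real and should be fixed. Its size can be stated only as a set of cases. After DLI, in a GVHD-free cohort of three and under the full DLT list, the two texts agree at zero non-GVHD DLTs and disagree at one, two or three. This count does not carry over to level 1, where infusional toxicity also withholds the go-ahead. In the other direction they disagree when there is grade 1-2 GVHD, or at level 1 a mild infusion reaction, without any DLT. The permissive half rests on the full DLT list being the intended one.

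The MTD definition (at most one patient in six with DLT) and the accrual of 4 to 20 per cohort are unaffected. No added harm is quantified, and none is shown to follow from the higher DLI dose for the omitted daratumumab-related events.

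**What to change.** 1. In the synopsis Enrollment schedule row, replace both go-ahead sentences with: *Escalation follows the DLT-count table in section 16, after the DLT observation period is complete for all patients in the cohort.* Keep the statement that three patients at a time may be enrolled at a level.
2. Conform the synopsis row headed Dose-limiting toxicity and the opening sentence of section 9.6 to the full DLT list, so that one definition applies throughout.

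The cost is an amendment to the wording of one synopsis row and two DLT statements. It needs no patients or procedures beyond those section 16 already requires.
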